4.1.1 Screening

Screening will determine participant eligibility for the study and begins when the participant signs the study informed consent form (ICF). Potential participants will initiate screening up to 4 weeks prior to dosing. The required screening evaluations for participants in the study are outlined in the Schedule of Assessments (SOA; [Section 1.3](#)).

Screening assessments can occur on multiple days, provided they are within the Screening period (Day -28 up to Day -2). The Investigator will determine whether participants meet eligibility criteria (see [Section 5.1](#) and [Section 5.2](#)).

For management of screen failures, refer to [Section 5.3](#).

4.1.2 Treatment

Period 1: Single Ascending Dose

Period 1 will evaluate single ascending doses of WVE-006 in up to five cohorts of up to 8 healthy participants each. Each cohort will include up to 6 WVE-006-treated and 2 placebo-treated participants (3:1 active:placebo). Participants will receive a single SC dose of WVE-006 or placebo on Day 1.

CCI

A sentinel strategy will be employed for the first 2 participants (1 active, 1 placebo) of every new dose level during the SAD portion of the study. The sentinel participants will be dosed and monitored in the clinic for 48 hours to identify any potential acute safety events. If neither of these sentinel participants experiences stopping criteria and if there are no other safety concerns during this 48-hour period, the remaining 6 participants will be randomized in a blinded fashion to active study drug (n=5) or placebo (n=1) and may be dosed on the same day. These participants will be observed in clinic for 48 hours after administration of study drug. Participants will attend weekly clinic visits on Weeks 0 through 12 to be followed for safety, tolerability, and PK assessments through Day 85 per the SoA.

If Period 1 Dose Escalation Stopping Criteria (see [Section 4.1](#)) are met at any point, dosing will be paused until further review and confirmation by the DMC. No further dosing will take place until after submission and approval of a substantial amendment if the DMC recommends the trial can continue.

Period 2: Multiple Doses

In Period 2, a single cohort of up to 8 healthy participants, including up to 6 WVE-006 and up to 2 placebo treated participants (3:1 active:placebo), will participate in a multidose assessment of WVE-006. A sentinel strategy will be employed for the first 2 participants (1 active:1 placebo), with a 48-hour observation period to assess for acute safety events. The DEC and DMC will review available safety and PK data from Period 1 to select the MTD with an acceptable PK profile. The MTD is defined as the dose below a dose level where any of the dose escalation stopping rules were met. If MTD is not achieved in Period 1 (i.e., no dose escalation stopping rules were met and all doses were well tolerated), then the highest dose reached in Period 1 will likely be selected for Period 2, though the DEC and DMC may select a lower dose based on all available information. At least 4 weeks of safety data for the proposed dose and all available data from the study must be available from Period 1 in order to inform the DEC and DMC Period 2 dose selection. WVE-006 or placebo will be administered every other week (Q2W) over 4 weeks (total of 3 doses; Weeks 0, 2, and 4). Following the first dose (Week 0) and last dose (Week 4), participants will stay in the clinic for at least two nights for PK assessments. Following the second dose (Week 2) all participants will be observed for safety evaluation in the clinic for at least 4 hours post-study drug administration or per local SOP (whichever is longer).

In Period 2, dosing will be paused or discontinued (per Investigator judgment) for an individual participant; see [Section 7.1.1](#) for additional details.

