Period 1 will evaluate single ascending doses of WVE-006 in up to five cohorts of up to 8 healthy participants each. An additional cohort (Cohort 6) may be included to evaluate concentration-QTc. Each cohort will include up to 6 WVE-006-treated and up to 2 placebo-treated participants (3:1 active:placebo). Participants will receive a single subcutaneous (SC) dose of WVE-006 or placebo on Day 1.

The starting dose and dose escalation are designed based on the following considerations:

CCI

The Dose Escalation Committee (DEC) and the Data Monitoring Committee (DMC) will review available safety and PK data through Day 8 for each dose cohort in combination with all available, previously accumulated safety data, as well as available PK data from participants enrolled in the study to date, to recommend subsequent dose escalation.

A sentinel strategy will be employed for the first 2 participants (1 active:1 placebo) of every new dose level during the SAD portion of the study. The sentinel participants will be dosed and monitored in the clinic for a minimum of 48 hours to identify any potential acute safety events. If neither of these sentinel participants experiences stopping criteria and if there are no other safety concerns during this 48-hour period, the remaining 6 participants will be randomized in a blinded fashion to active study drug (n=5) or placebo (n=1) and may be dosed on the same day. These participants will be observed in clinic for 48 hours after administration of study drug. Participants will attend weekly clinic visits on Weeks 0 through 12 to be followed for safety, tolerability, and PK assessments through Day 85 per schedule of assessments (SoA).

Period 2

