1.2 Protocol Schema

1.3 Schedule of Assessments**Table 1 Overall Schedule of Assessments (Period 1)**

	Screening Period ^a	Dosing- CRU Stay				Follow-up				ET
Visit	1	2				3, 4, 5, 7, 8, 9, 11, 12, 13	6	10	14	
Study Week	Week -4 to Week 0	Week 0				Week 1, 2, 3, 5, 6, 7, 9, 10, 11	Week 4	Week 8	Week 12	
Study Day Event/Assessment	Day -28 to Day -2	Day -1	Day 1	Day 2	Day 3	Day 8, 15, 22, 36, 43, 50, 64, 71, 78 (±3 days)	Day 29 (±3 days)	Day 57 (±3 days)	Day 85 (±5 days)	
Informed Consent	X									
Demographics	X									
Medical History	X									
Prior/concomitant medications	X	X	X	X	X	X	X	X	X	X
Admission to CRU		X								
Discharge from CRU					X					
Eligibility Criteria/Recheck	X	X								
AAT Genetic Testing	X									
Serum Pregnancy Test ^b	X								X	X
Urine Pregnancy Test ^b		X			X	X	X	X		
FSH ^c	X									
Viral Serology	X									
COVID-19 Testing ^d	X	X								

	Screening Period ^a	Dosing- CRU Stay				Follow-up				ET
Visit	1	2				3, 4, 5, 7, 8, 9, 11, 12, 13	6	10	14	
Study Week	Week -4 to Week 0	Week 0				Week 1, 2, 3, 5, 6, 7, 9, 10, 11	Week 4	Week 8	Week 12	
Study Day Event/Assessment	Day -28 to Day -2	Day -1	Day 1	Day 2	Day 3	Day 8, 15, 22, 36, 43, 50, 64, 71, 78 (±3 days)	Day 29 (±3 days)	Day 57 (±3 days)	Day 85 (±5 days)	
Safety Laboratory ^c	X	X		X	X	X	X	X	X	X
Plasma PK and Select Labs ^f			X	X	X	X	X	X	X	X
Urine PK sample ^f			X	X	X	X	X	X	X	X
Serum Sample for Immunogenicity		X					X	X	X	X
Full Physical Exam ^g	X	X			X		X	X	X	X
Symptom-directed Physical Exam ^g			X	X		X				
Body Weight/BMI ^h	X	X		X	X	X	X	X	X	X
Height	X									
Vital Signs ⁱ	X	X	X	X	X	X	X	X	X	X
Digital Continuous and Triplicate 12-lead ECG ^j	X	X		X	X				X	X
Urine Drug Screen ^k ; Cotinine; Alcohol Breath or Urine Test	X	X				X	X	X	X	X
Study Drug Administration SC Injection			X							

	Screening Period ^a	Dosing- CRU Stay				Follow-up				ET
Visit	1	2				3, 4, 5, 7, 8, 9, 11, 12, 13	6	10	14	
Study Week	Week -4 to Week 0	Week 0				Week 1, 2, 3, 5, 6, 7, 9, 10, 11	Week 4	Week 8	Week 12	
Study Day Event/Assessment	Day -28 to Day -2	Day -1	Day 1	Day 2	Day 3	Day 8, 15, 22, 36, 43, 50, 64, 71, 78 (±3 days)	Day 29 (±3 days)	Day 57 (±3 days)	Day 85 (±5 days)	
Adverse Event Monitoring	X	X	X	X	X	X	X	X	X	X

Abbreviations: AAT = alpha-1 antitrypsin; BMI = body mass index; CRU = clinical research unit; ECG = electrocardiogram; ET = early termination; FSH = follicle stimulating hormone; PK = pharmacokinetic; SC = subcutaneous.

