^a Screening assessments can occur on multiple days, provided they are within the Day -28 up to Day -2 Screening period.

^b Negative serum pregnancy test at Screening for women of childbearing potential (WOCBP). Negative highly sensitive urine pregnancy test documented for WOCBP on Day -1.

^c FSH only to confirm non-childbearing potential.

^d COVID-19 testing if required per site SOPs.

^e Safety laboratory tests include hematology, clinical chemistry, coagulation and urinalysis as noted in [Table 11](#). Note that for urinalysis, abnormal results on dipstick or urinalysis should lead to laboratory urinalysis testing and/or urine microscopy. Any specific safety labs indicated in [Table 2](#) will be collected according to the schedule in that table. When applicable and feasible, blood sampling should follow evaluations of vital signs and ECGs to reduce any impact on these measurements.

^f Specific time points for PK and select laboratory assessments provided in [Table 2](#) and [Table 3](#). Participants should stay in the clinic for 48 hours after dose to complete assessments.

^g Full physical examination includes (at a minimum): alertness and orientation, general appearance, skin, head, eyes, ears, nose, throat, lungs, cardiovascular, gastrointestinal, musculoskeletal, and neurologic systems. Symptom-directed physical exams to be performed by visit as necessary.

^h Height at Screening will be used for BMI calculations at all visits.

ⁱ Vital signs will be taken with the participant in the supine position after ≥5 minutes of rest. Temperature, respiratory rate, and percent oxygen saturation in the blood (SpO₂) are measured once per time point. Blood pressure (systolic and diastolic) and pulse: measured ≤30 minutes pre-dose and 1 hr (±10 min), 2 hr (±10 min), 4 hr (±20 min), 12 hr (±1 hr) post dose on Day 1 and once at all other noted visits.

^j Continuous digital ECG monitoring for at least 48 hours from Day -1 through Day 2; leads may be disconnected for ~20 minutes at 24 hours after dosing to allow for participant cleansing. Additional triplicate 12-lead ECGs are specified in [Table 4](#). Participant must rest quietly for ≥5 minutes prior to triplicate ECGs.

^k For drug screen panel, see [Table 11](#) other screening tests.

Table 2 Plasma PK and Selected Laboratory Time Points (Period 1)

Visit	2											3	4	5 through 14
Study Day/ Specific Time/ Window	Day 1								Day 2		Day 3	Day 8	Day 15	Weeks 3 through 12

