4 STUDY DESIGN

4.1 Overall Study Design

This is a double-blind, placebo-controlled, single ascending dose (SAD) and multidose Phase 1 study to assess the safety, tolerability, and PK of WVE-006 in healthy participants. Participants will be randomized to WVE-006 or placebo.

Period 1 will evaluate single ascending doses of WVE-006 in up to five cohorts of up to 8 healthy participants each (3:1 active:placebo). An additional cohort (Cohort 6) may be included to evaluate concentration-QTc. Participants may be on-study for up to 12 weeks. A sentinel strategy will be employed for the first 2 participants (1 active:1 placebo) of every new dose level during the SAD portion (Period 1) and in the multiple dose portion (Period 2) of the study, with a 48-hour observation period to assess for acute safety events. The Dose Escalation Committee (DEC) and the DMC will review available data through Day 8 that will include key PK parameters and safety for each dose cohort, as well as previously accumulated safety data and available PK data, to recommend subsequent dose escalation. Additional details are provided in [Section 4.1.2](#).

Dose Escalation Stopping Criteria (Period 1):

Dose escalation will be paused until further evaluation by the DMC if any of the following criteria are met. If it is confirmed that a stopping criterion was met, no further dosing will take place until after submission and approval of a substantial amendment if the DMC recommends the trial can continue.

- One or more at least possibly related Common Terminology Criteria for Adverse Events (CTCAE) Grade ≥ 3 TEAE or CTCAE grade ≥ 3 laboratory abnormality in a single cohort.
 - All grade 3 toxicities for vital signs must be confirmed with a repeat measurement obtained within 1 hour.
 - All grade 3 toxicities for laboratory parameters must be confirmed with a repeat measurement obtained within 24 hours.
- Two or more at least possibly related CTCAE grade ≥ 2 TEAEs or CTCAE Grade ≥ 2 laboratory abnormalities in a single cohort.
 - All grade 2 toxicities for vital signs must be confirmed with a repeat measurement obtained within 1 hour.
 - All grade 2 toxicities for laboratory parameters must be confirmed with a repeat measurement obtained within 24 hours.
- Any at least possibly related SAE in a single cohort.

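### Period 1: the other six participants can be dosed at 48 hours before the sentinels' last in-clinic laboratory samples are drawn or read

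*Combined protocol and SAP*

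**What the plan says.** Section 4.1.2 and the synopsis (1.1) describe the same sentinel step for Period 1. The first two participants at each new dose level, one active and one placebo, are dosed ahead of the rest. In the synopsis, "The sentinel participants will be dosed and monitored in the clinic for a minimum of 48 hours". The other six (five active, one placebo) may then be dosed on a single day "If neither of these sentinel participants experiences stopping criteria and if there are no other safety concerns during this 48-hour period".

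The Period 1 stopping criteria in section 4.1 include laboratory findings. One is a "CTCAE grade ≥ 3 laboratory abnormality in a single cohort", with this condition: "All grade 3 toxicities for laboratory parameters must be confirmed with a repeat measurement obtained within 24 hours". Findings of Grade 2 or higher count when there are two or more.

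The sampling schedule is in section 1.3:

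- Table 2 puts blood count, CRP, fibrinogen, coagulation and albumin at 6 h (±10 min), 24 h (±30 min) and 48 h (±4 h) after dosing.
- Table 1 marks the "Safety Laboratory" row on Days 2 and 3, without a clock time. Footnote e gives the content: "Safety laboratory tests include hematology, clinical chemistry, coagulation and urinalysis as noted in" Table 11.
- Footnote f of Table 1 says: "Participants should stay in the clinic for 48 hours after dose to complete assessments".

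Section 10.2 requires the Investigator to document review of every laboratory safety report, without a deadline. Section 4.1.2 adds that if the Period 1 stopping criteria "are met at any point, dosing will be paused until further review and confirmation by the DMC".

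**The concern.** The release condition is partly a laboratory condition, because laboratory abnormalities are stopping criteria. It is tied to elapsed time, however, and not to results being in hand. A sample not yet drawn, or drawn and not yet reported, cannot show that a criterion is met. A site that follows the text exactly can therefore treat the condition as satisfied at 48 h while the last in-clinic sentinel results are outstanding.

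The sentinel step is the within-cohort protection at each new dose level of a first-in-human drug given to healthy volunteers. If the one active sentinel has a Grade 3 value on the 48-hour sample, that value once confirmed would have stopped the dosing of the other six. If they have already had their single injection, the pause in section 4.1.2 has nothing left to stop in that cohort.

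**Working it through.** The plan gives no figure to reproduce for this point. The cohort split is consistent: 1 + 5 = 6 active and 1 + 1 = 2 placebo, which is 3:1.

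**Inputs.** Release possible from 48 h (1.1, 4.1.2). Draw windows from Table 2. Repeat within 24 h (4.1). Laboratory turnaround T is not stated; I assume T = 2 to 24 h. Times below are hours after the sentinel's dose.

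**1. When can the last draw fall?** 48 − 4 = 44 h to 48 + 4 = 52 h. The latest permitted draw is 52 − 48 = 4 h after release becomes possible.

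**2. How fast must the laboratory be for a first result to be known by 48 h?** Longest allowable T = 48 h − draw time.

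| Draw | Time of draw | Longest T |
|---|---|---|
| 6 h, latest | 6 h 10 min | 41 h 50 min |
| 24 h, latest | 24.5 h | 23.5 h |
| 48 h, earliest | 44 h | 4 h |
| 48 h, drawn at 46 h | 46 h | 2 h |
| 48 h, drawn at 48 to 52 h | 48 to 52 h | none |

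The 6 h results are known over the whole assumed range, and the 24 h results over nearly all of it. A 48-hour sample drawn on time or late cannot be known at 48 h at any turnaround.

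**3. When are the 48-hour results known?** Draw time + T: 44 + 2 = 46 h to 52 + 24 = 76 h. That is from 48 − 46 = 2 h before to 76 − 48 = 28 h after release becomes possible. For a draw at exactly 48 h: 50 to 72 h, or 2 to 24 h after.

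**4. When is a repeat known?** Section 4.1 does not say whether the 24 hours run from the first draw or from its result.

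- From the first draw: repeat drawn by 44 + 24 = 68 h to 52 + 24 = 76 h; result by 68 + 2 = 70 h to 76 + 24 = 100 h, so 22 to 52 h after the 48-hour point.
- From the result: repeat drawn by 46 + 24 = 70 h to 76 + 24 = 100 h; result by 70 + 2 = 72 h to 100 + 24 = 124 h, so 24 to 76 h after the 48-hour point.

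These are latest times; a prompt repeat shortens them.

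**5. What the window does not cover.** The ±4 h belongs to Table 2, where albumin is the only chemistry test. ALT, AST and GLDH come from the Table 1 panels on Days 2 and 3, which have no clock time. Steps 1 to 4 apply to Day 3 chemistry only if it is taken with the 48-hour draw.

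**6. How many people pass this step?** Five cohorts: 5 × 6 = 30 participants, 5 × 5 = 25 active. With optional Cohort 6 at a new dose level: 6 × 6 = 36 and 6 × 5 = 30.

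**The case against.** The best defence is that the release condition already contains the laboratory criteria. An Investigator who knows that a result is due could hardly declare that no criterion has been met without it. Review of every report is required, 48 hours is a minimum in the synopsis, and dosing the other six is permitted rather than obliged. This is a reasonable reading, and some sites will follow it. It remains an implied duty, which up to four units may apply differently. The protocol does state data-availability rules elsewhere: four weeks of safety data must be available before the Period 2 dose is chosen, and Table 2 footnote b says a participant's own pre-dose results need not be awaited.

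The second defence is that little is left uncovered, and this largely stands. The sentinel step targets acute events. The 6 h and 24 h blood tests, the Day 2 chemistry, vital signs and serial ECGs all precede 48 h. A reader might infer that the other six are dosed without regard to sentinel laboratory data, or that a known Grade 3 value could be passed over. The documents support neither: a known value falls under the stopping criteria or the clause on other safety concerns.

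Two further points are fair. The turnaround range is an assumption, and with an early draw and a fast laboratory there is no gap. The Study Manual, Laboratory Manual and committee charters are not public and could hold a release rule. The redacted text ahead of the sentinel paragraph in 4.1.2 probably concerns the maximum dose, since 4.3 and Table 9 refer to 4.1.2 for it, but a laboratory rule there cannot be excluded.

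The Day 8 committee review does not answer the point, because it governs escalation to the next cohort and not release within a cohort.

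**Conclusion.** The point holds in a limited form. In Period 1, no visible text ties the sentinels' laboratory results to the release of the other six, and the permitted draw window lets release come before the last in-clinic sample is drawn. The gap is confined to the 48-hour/Day 3 results and any confirmatory repeat still pending. At the assumed turnaround of 2 to 24 h, the 48-hour results arrive between 2 h before and 28 h after release becomes possible. For Day 3 chemistry no range can be given from the current text.

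A reader might take the 30 participants (25 active), or 36 (30 active) with Cohort 6, as the number put at risk. They are only the most who pass this step. The documents give no rate of laboratory toxicity, so no probability of harm can be derived.

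The change should be made, because it acts on when people are dosed and costs little. Period 2 has the same sentinel wording but is left out. Its dose will already have been given in Period 1 with at least four weeks of safety data, and the graded laboratory criteria in 4.1 are labelled for Period 1.

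**What to change.** Add to the Period 1 text in both 1.1 and 4.1.2:

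> The remaining 6 participants will not be dosed until the sentinels' safety laboratory results (hematology, coagulation, clinical chemistry) through the 48-hour/Day 3 draw, with the Day 3 chemistry taken at the 48-hour draw, have been reported and reviewed by the Investigator; if a value would meet a Period 1 stopping criterion once confirmed, dosing is held until the repeat is back. Cytokine and complement results need not be awaited.

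The last sentence is needed because Table 11 lists complement under hematology. A lone Grade 2 value does not trigger the hold.

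No scheduled samples are added. The cost is a delay of about 0 to 28 h per cohort at the assumed turnaround. Only if a repeat is pending does it grow, to at most 22 to 52 h or 24 to 76 h after the 48-hour point, depending on which event starts the repeat clock. If the other six have already been admitted, some Day -1 checks (safety laboratory tests, pregnancy, drug and alcohol tests, ECG) may have to be repeated; scheduling their admission after the sentinel results would avoid most of this.

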4.1.3 Follow-up

Following completion of study treatment, participants will continue to have follow-up visits for up to 12 weeks. Safety assessments will be completed and safety laboratory samples, and PK samples will be drawn during these visits. Refer to [Table 1](#) for Period 1 and [Table 5](#) for Period 2 details.

4.1.4 Early Termination

If a participant withdraws from the study early, the participant should complete an early termination (ET) visit. Assessments to be performed at the ET visit are detailed in [Table 1](#) for Period 1 and [Table 5](#) for Period 2. Refer to [Section 7](#) for information on early withdrawal from study drug or from the study.

4.2 Scientific Rationale for Study Design

A double-blind, placebo-controlled study will ensure unbiased assessment of safety and tolerability of WVE-006 SC injection. The single ascending doses in Period 1 will provide the best opportunity to determine a safe and potentially efficacious dose to bring forward into Period 2 and additional clinical studies.

4.3 Justification for Dose

Initial Dose

As described in the International Council for Harmonization (ICH) M3(R2) guideline, the selection of the first-in-human (FIH) dose and dose escalation plan will not be higher than that supported by NOAELs from the 5-week interim data of the GLP 13-week repeat dose toxicity studies in mice and cynomolgus monkeys. Selected doses were based on the totality of the data for both mouse and cynomolgus monkey, including the NOAEL provided by the GLP toxicity studies, projected pharmacologically active dose and assessment for potential QTc prolongation risks. The initial dose was selected using the most relevant approaches described in:

- US Food and Drug Administration (USFDA) guidance for industry: [Estimating the Maximum Safe Starting Dose in Initial Clinical Trials for Therapeutics in Adult Healthy Volunteers](#) (2005).
- European Medicines Evaluation Agency (EMA) [Guideline on strategies to identify and mitigate risks for first-in-human and early clinical trials with investigational medicinal products](#) (2017)

CCI [REDACTED] Two interspecies scaling approaches were used for HED and safety margin projection, a conservative approach based on body surface area (BSA) scaling ([FDA, 2005](#)), as well as an empirical approach based on body weight supported by literature, which showed a 1:1 body-weight-based conversion factor from monkey to human and an approximately 1:7 body-weight-based conversion factor from mouse to human for plasma exposure ([Nanavati et al., 2021](#); [Wang et al., 2019](#)).

The pharmacological activities of WVE-006 are not expected in HV CCI [REDACTED]

Dose Escalation

CCI

The planned initial dose for Period 1 is 30 mg (Period 1, Cohort 1). Subsequent dose levels will be determined by the DEC and DMC based on previous Period 1 cohort data and will not exceed a CCI increase of the prior dose. The maximum dose will not exceed the limit specified in [Section 4.1.2](#). Dosing decisions will be communicated directly to the site.

CCI

If adequate safety and tolerability is observed in the initial dose cohorts (Cohorts 1 to 5) and no cohort stopping criterion was met, an optional cohort (Cohort 6) may be conducted in order to characterize the safety, tolerability, PK and the relationship between drug concentration and QTc prolongation at an appropriate dose.

The MTD level from Period 1 will be selected to be explored in Period 2. If the MTD is not achieved in Period 1 and the top dose is well tolerated, then the top dose will likely be selected for Period 2. The projected PK/PD profiles support every other week dosing regimen, but this recommendation is subject to change once clinical data become available. The DEC and DMC may select a lower dose based on all available information.

The exposures of the selected doses during Period 1 and Period 2 of the study will not exceed the observed exposures at the NOAEL.

